6.8 Compliance

The patient must attend his/her post-operative appointments in the ninety days after surgery to evaluate for any signs of delayed gastric emptying.

7 SAFETY EVALUATION

7.1 Clinical Events of Interest and Adverse Events

Clinical events of interest (captured in REDCap) include, but are not limited to: patient continues to require supplemental jejunal feeds, persistent clinical symptoms of delayed gastric emptying (delayed gastric emptying assessed by the gastrografin swallow exam/CT esophagram), subsequent pneumonia, aspiration events, respiratory failure requiring reintubation, nausea, vomiting, ability to eat solid food or drink liquids or having any trouble eating, early satiety, difficulty swallowing saliva, bile or green staining on pillow while sleeping, experiencing acid indigestion or heartburn, pain with eating, additional postop procedures, EORTC QLQ-30 QoL scores, and hospital length of stay.

7.1.1 Definition of Adverse Events

An adverse event or adverse experience (AE) is any untoward medical occurrence associated with the use of a drug in humans, whether or not considered drug related. Therefore, an AE can be ANY unfavorable and unintended sign (including an abnormal laboratory finding), symptom, or disease temporally associated with the use of a medicinal (investigational) product, whether or not considered related to the medicinal (investigational) product (attribution of ‘unrelated’, ‘unlikely’, ‘possible’, ‘probable’, or ‘definite’).

An AE is considered “unexpected” if it is not listed in the investigator brochure or is not listed at the specificity or severity that has been observed; or if an investigator brochure is not required or available, is not consistent with the risk information described in the general investigational plan in other study-related documents.

7.1.1.1 Diagnosis Versus Signs and Symptoms

If known, a diagnosis should be recorded on the CRF rather than individual signs and symptoms (e.g., record only liver failure or hepatitis rather than jaundice, asterixis, and elevated transaminases). However, if a constellation of signs and/or symptoms cannot be clinically characterized as a single diagnosis or syndrome at the time of reporting, each individual event should be recorded as an AE or SAE on the CRF. If a diagnosis is subsequently established, it should be reported as follow-up information.

7.1.1.2 Adverse Events Occurring Secondary to Other Events

In general, AEs occurring secondary to other events (e.g., cascade events or clinical sequelae) should be identified by their primary cause. For example, if severe diarrhea is known to have resulted in dehydration, it is sufficient to record only diarrhea as an AE or SAE on the CRF.

However, clinically significant AEs occurring secondary to an initiating event that are separated in time should be recorded as independent events on the CRF. For example, if a severe gastrointestinal hemorrhage leads to renal failure, both events should be recorded separately on the CRF. Pain will not be considered an adverse event at any point, given the nature of the intervention (surgical procedure).

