7.2 Serious Adverse Events

7.2.1 Definition

A serious adverse event (SAE) is any adverse event (experience) that in the opinion of either the investigator or sponsor results in **ANY** of the following:

- Death.
- A life-threatening adverse event (experience). Any AE that places a participant or participants, in the view of the Investigator or sponsor, at immediate risk of death from the reaction as it occurred. It does **NOT** include an AE that, had it occurred in a more severe form, might have caused death.
- Inpatient hospitalization or prolongation of existing hospitalization (for > 24 hours).
- A persistent or significant incapacity or substantial disruption of the ability to conduct normal life functions.
- A congenital anomaly or birth defect.
- Important Medical Event (IME) that, based upon medical judgment, may jeopardize the participant and may require medical or surgical intervention to prevent one of the outcomes listed above.

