7.2.2 Reporting Serious Adverse Events

All new SAEs occurring from the date the participant signs the study consent until 90 days after the last intervention or a new treatment is started, whichever comes first, will be reported. The RPCI SAE Source Form is to be completed with all available information, including a brief narrative describing the SAE and any other relevant information.

SAEs occurring after the 90 day follow-up period that the investigator determines to be possibly, probably or definitely related to the study intervention should be reported.

SAEs that are unexpected and possibly, probably or definitely related must be reported as an Unanticipated Problem. Please refer to **Section 7.4** for details on reporting Unanticipated Problems.

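### Section 7.1.1.2 excludes all pain from adverse events without exception, so undiagnosed pain that meets a seriousness criterion falls outside SAE reporting

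*Combined protocol and SAP*

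**What the plan says.** The rule on pain closes Section 7.1.1.2, which otherwise deals with events secondary to other events: "Pain will not be considered an adverse event at any point, given the nature of the intervention (surgical procedure"). The surgical nature of the intervention is the only reason given, and no other section limits the rule or adds an exception.

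Four other provisions bear on it:

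- Section 7.1.1, the general definition: "an AE can be ANY unfavorable and unintended sign (including an abnormal laboratory finding), symptom, or disease temporally associated with" use of the product, whether or not it is considered related.
- Section 7.1.1.1, for signs and symptoms that cannot be characterized as one diagnosis when reported: "each individual event should be recorded as an AE or SAE on the CRF".
- Section 7.2.1: "A serious adverse event (SAE) is any adverse event (experience) that in the opinion of either the investigator or sponsor results in" one of the listed outcomes, among them "Inpatient hospitalization or prolongation of existing hospitalization (for > 24 hours").
- Section 7.2.2, on what is reported: "All new SAEs occurring from the date the participant signs the study consent until 90 days after the last intervention", or until a new treatment starts if that is earlier. Within that window relatedness is not required.

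Pain also appears outside the AE system. Section 7.1 includes it among the clinical events of interest held in REDCap: "experiencing acid indigestion or heartburn, pain with eating, additional postop procedures". The day-90 call (Section 6.7) asks about pain with eating, Appendix C item 6 asks about it at the emptying study, and OES18 items 46 to 48 (Appendix D) ask about pain when eating, in the chest and in the stomach.

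**The concern.** Leaving out expected pain after an esophagectomy is a sensible way to keep the AE log readable. This sentence goes further. It removes pain of every grade, site and cause for the whole study, in both arms, and keeps no exception for pain that is itself serious.

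Two things are at stake. The first is reporting: an event that puts a participant back in hospital could properly go unreported by staff who follow the text. The second is the safety comparison. Both arms have the operation and only one has the pyloric injection, so surgery common to both arms is no reason to leave out pain that might differ between them. Section 1.2 gives avoidance of the drug's side effects as one possible benefit of omitting the injection, so the AE record should be able to show such effects or their absence.

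**Working it through.** No arithmetic applies. The plan gives no figure on this point and none is needed. The check sets the sections side by side and follows types of event through them.

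**The chain of definitions**

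1. Under 7.1.1 any unfavorable, unintended symptom is an AE, related or not. Pain is a symptom.
2. Under 7.1.1.1 a symptom without a diagnosis is recorded in its own right, as an AE or SAE.
3. Under 7.1.1.2 pain is never an AE. This reverses steps 1 and 2 for pain.
4. Under 7.2.1 an SAE is an adverse event with a listed outcome. What is not an AE cannot be an SAE.
5. Section 7.2.2 reports SAEs. An event stopped at step 4 does not reach it.

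**Which events are lost**

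| Event | Outcome as written |
|---|---|
| Pain for which a diagnosis is made | The diagnosis is recorded (7.1.1.1), and is an SAE if serious. Not lost. |
| Undiagnosed pain with other symptoms, such as vomiting or dysphagia | The other symptoms remain recordable; the pain does not. |
| Pain alone, undiagnosed, meeting a 7.2.1 criterion such as hospitalization | Not an AE, so not an SAE. Lost to 7.2.2. |
| Pain alone, undiagnosed, Grade 3 or 4, not serious | The 7.1.4 table would require reporting at any attribution. Lost. |
| Pain alone, Grade 1 or 2, at least possibly related | The 7.1.4 table would require reporting. Lost. |
| Pain alone, Grade 1 or 2, unrelated or unlikely | Not reportable under 7.1.4 in any case. The sentence changes nothing. |
| Emergency assessment for pain, with no admission and no other listed outcome | Not serious under 7.2.1 in any case. |

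The third row is the important one. The fourth and fifth rows are lost from grading and attribution (7.1.3), routine reporting (7.1.4) and the tables by grade (9.4.1).

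**Windows.** Section 7.1.4 frames routine AE reporting as running to 30 days after the last intervention, although Table 2 and Section 6.7 still list AEs at the day-90 call. The clear 90-day window is the one for SAEs in 7.2.2.

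**Does another route bring the serious case back?** Only in part. An Unanticipated Problem (7.4.1) may be any incident or outcome, but it must be unexpected, at least possibly related, and suggest greater risk than was known. The alternative to the last condition, seriousness under 7.2, is worded for an AE, and pain has been ruled out as one. SAE reporting within its window asks for neither relatedness nor unexpectedness.

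**Do the other pain data replace AE reporting?** The OES18 is given once, around Postoperative Visit #2, and covers the past week. Appendix C covers one test session. The day-90 call and the named clinical event of interest concern pain with eating, though the list in 7.1 is not exhaustive. None is stated to lead to CTCAE grading, attribution or an SAE form.

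**The case against.** The strongest reply is that a specific rule may qualify a general one. Section 7.1.1 counts abnormal laboratory findings, yet 7.1.1.3 records only those that are clinically significant and need active management. Section 7.1.1.4 likewise limits preexisting conditions. The pain sentence can be read as a third deliberate carve-out with a stated reason. This stands as far as it goes: narrowing the definition is not in itself an error. But the other two carve-outs keep the important cases, namely abnormalities that need management and conditions that worsen. The pain sentence keeps none.

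Second, pain is not invisible. The questionnaires, the clinical events of interest and the day-90 call collect it in both arms. Section 9.4 plans a between-arm comparison of quality-of-life scores, whereas 9.4.1 plans only AE frequencies by grade and names no between-arm test. This stands. A reader might infer that the trial cannot show any difference in pain between arms, and the documents do not support that.

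Third, a reader might infer that the monitoring committee would see no pain data, because Section 11.1 sends AE data to a separate system for committee reporting. That is not supported either. Sections 8 and 9.4.1 say the committee reviews the safety data and critical efficacy endpoints, and nothing says that clinical events of interest are withheld.

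Fourth, Section 7.1.2 does not list pain among the expected effects of the toxin, so a difference between arms is not predicted. This is fair, and the point does not assume one. AE recording under 7.1.1 does not depend on an effect being expected.

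Last, staff might report serious pain regardless. They would then be acting against the written rule, and at their discretion. The surgeon knows the allocation (Section 4.1), so such reporting could differ by arm.

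**Conclusion.** The point holds in a narrow form. As written, undiagnosed pain that meets a seriousness criterion is outside SAE reporting, and severe or possibly injection-related pain is outside AE grading, attribution and tabulation. Sections 7.1.1.2, 7.1.1, 7.1.1.1 and 7.2.1 must be reconciled.

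The size cannot be stated as a count: the documents give no rate of pain events or of pain-related readmission. The primary endpoint, sample size, power and type I error are unaffected. The conclusion rests on a literal reading of the sentence and of the SAE definition as a subset of AEs.

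Two wider readings are not supported. A reader might take every emergency assessment for pain to be a lost SAE, but assessment alone is not a criterion in 7.2.1. A reader might also take all pain over 90 days to be lost from AE reporting, but 7.1.4 frames routine reporting as 30 days after the last intervention and requires Grade 1 and 2 events only when at least possibly related. The sentence is still worth amending, because following it exactly could leave a serious event unreported.

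**What to change.** Amend the last sentence of Section 7.1.1.2 in two respects:

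- Limit the exclusion to expected procedural pain.
- State that any pain meeting a criterion in 7.2.1, and any pain not explained by the expected postoperative course, is recorded, graded and attributed like any other AE in both arms, within the existing windows and the grade/attribution rules of 7.1.4 and 7.2.2.

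Where to draw the line for expected pain, for example at the end of the index hospital stay, is for the sponsor to decide; the documents do not settle it. Whatever line is chosen should be written down and applied identically in both arms.

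The change needs a short amendment and no new assessment, visit or form. Its downside is a few more AE entries in a trial of at most 50 evaluable patients, and some judgement by the investigator on what counts as expected.

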7.1.1.3 Abnormal Laboratory Values

Only clinically significant laboratory abnormalities that require active management will be recorded as AEs or SAEs on the CRF (e.g., abnormalities that require study drug dose modification, discontinuation of study treatment, more frequent follow-up assessments, further diagnostic investigation, etc.).

If the clinically significant laboratory abnormality is a sign of a disease or syndrome (e.g., alkaline phosphatase and bilirubin 5 x the upper limit of normal associated with cholecystitis), only the diagnosis (e.g., cholecystitis) needs to be recorded on the Adverse Event CRF.

If the clinically significant laboratory abnormality is not a sign of a disease or syndrome, the abnormality itself should be recorded as an AE or SAE on the CRF. If the laboratory abnormality can be characterized by a precise clinical term, the clinical term should be recorded as the AE or SAE. For example, an elevated blood potassium level of 7 mEq/L should be recorded as “hyperkalemia.”

Observations of the same clinically significant laboratory abnormality from visit to visit should not be repeatedly recorded as AEs or SAEs on the CRF, unless their severity, seriousness, or etiology changes.

7.1.1.4 Preexisting Medical Conditions (Baseline Conditions)

A preexisting medical condition should be recorded as an AE or SAE only if the frequency, severity, or character of the condition worsens during the study. When recording such events on an Adverse Event CRF, it is important to convey the concept that the preexisting condition has changed by including applicable descriptors (e.g., “more frequent headaches”).

7.1.2 Drug Information- Botulinum toxin

OnabotulinumtoxinA (botulinum toxin type A, Botox[©]) inhibits the release of acetylcholine from nerve endings at neuromuscular junctions in the local muscle (10). Without the release of acetylcholine, neurotransmission between peripheral nerve endings and muscle fibers cannot occur, and the muscle becomes weak or paralyzed (10). The inhibitory effect of botulinum toxin is temporary, and muscle function recovers at 3 months after administration. The effect is not immediate, and rather occurs within 1-3 days.

With intramuscular injection at a dose of 100 units, botulinum toxin is not expected to be in contact with the peripheral blood (10). In rare instances, botulinum toxin may spread from the area of injection and produce symptoms consistent with botulinum toxin effects (13). These unanticipated symptoms may include asthenia, diplopia, ptosis, dysphagia, dysphonia, urinary incontinence, and breathing difficulties. These symptoms have been reported hours to weeks after injection.

Incidence of side-effects depends on injection site location. For example, patients treated with botulinum toxin injection into the sternocleidomastoid muscle for cervical dystonia are more likely to have the side-effects of swallowing difficulties, due to local diffusion. Swallowing and breathing difficulties may be life-threatening, and there have been reports of death (11). Patients with history of underlying conditions predisposing to muscle weakness have an increased risk of these side effects occurring (11). However, due to the nature of this study, patients with underlying muscle weakness are excluded from this study.

The maximum recommended dose of OnabotulinumtoxinA, regardless of the indication, is 400 units over three months (10). Cervical dystonia is treated with doses ranging from 198-300 units, divided among the affected muscle, with maximum dose 50 units per site. Our proposed dosage, 100 units in divided doses into the pyloric muscle, is within the range used among other high-volume esophagectomy centers (2, 3, 8, 9).

Absolute contraindications to botulinum toxin injection include previous hypersensitivity to the product (10). Mild to moderate side effects are generally mild transient, and include swelling or bruising at the injection site, and the small possibility of infection at injection site (10). Anaphylaxis/hypersensitivity reactions have occurred (11). Higher doses or more frequent administration may result in neutralizing antibody formation and loss of efficacy (10). This summary of the US FDA boxed warning may also be found at: <http://www.fda.gov/downloads/Drugs/DrugSafety/UCM176360.pdf>

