**INVESTIGATOR STUDY ELIGIBILITY VERIFICATION FORM
EXCLUSION CRITERIA**

Participant Name: _____

Medical Record No.: _____

Title: Double-arm, Randomized Study of Botulinum Toxin Injection as a Pyloric Drainage Procedure for Minimally Invasive Esophagectomy (Phase II)

EXCLUSION CRITERIA				
Yes	No	N/A	All answers must be "No" or "N/A" for participant enrollment.	Date
			1. Patients who have a history of gastrointestinal dysmotility or functional gastroparesis, including diabetic gastroparesis, central and peripheral nervous system disorders, renal failure, medication side effects, including chronic dependence of promotility agents, anticholinergic antispasmodic agents, or chronic narcotic use over 2 years due to non-cancer causes. Refer to Appendix B for a list of pharmacologic agents.	
			2. Patients who have a history of previous gastric or duodenal surgery.	
			3. Patients who have a history of duodenal ulcer or duodenal fibrosis.	
			4. Uncontrolled intercurrent illness including, but not limited to, ongoing or active infection, symptomatic congestive heart failure, unstable angina pectoris, cardiac arrhythmia, or psychiatric illness/social situations that would limit compliance with study requirements.	
			5. Allergy to botulinum toxin, and or egg	
			6. Pregnant or nursing female participants.	
			7. Unwilling or unable to follow protocol requirements.	
			8. Any condition which in the Investigator's opinion deems the participant an unsuitable candidate for study participation.	

Participant meets all entry criteria:

Yes **No**

If "NO", do not enroll participant in study.

Investigator Signature: _____ **Date:** _____

Printed Name of Investigator: _____

TABLE OF CONTENTS

1	Background	11
1.1	Minimally Invasive Esophagectomy for Esophageal Carcinoma.....	11
1.2	Risks and/or Benefits.....	12
2	Rationale.....	13
3	Objectives.....	13
3.1	Primary Objective.....	13

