5.2 Exclusion Criteria

Participants will be excluded from this study for the following:

1. Patients who have a history of gastrointestinal dysmotility or functional gastroparesis, including diabetic gastroparesis, central and peripheral nervous system disorders, renal failure, medication side effects, including chronic dependence of promotility agents, anticholinergic antispasmodic agents, or chronic narcotic use over 2 years due to non-cancer causes. Refer to **Appendix B** for a list of pharmacologic agents.
2. Patients who have a history of previous gastric or duodenal surgery.
3. Patients who have a history of duodenal ulcer or duodenal fibrosis.
4. Uncontrolled intercurrent illness including, but not limited to, ongoing or active infection, symptomatic congestive heart failure, unstable angina pectoris, cardiac arrhythmia, or psychiatric illness/social situations that would limit compliance with study requirements.
5. Allergy to botulinum toxin, and or egg.
6. Pregnant or nursing female participants.

7. Unwilling or unable to follow protocol requirements.
8. Any condition which in the Investigator's opinion deems the participant an unsuitable candidate for study participation.

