6.2 Baseline Evaluations

Preoperative workup and multimodality therapy for esophageal cancer as standard of care at RPCI, based upon the NCCN guidelines for esophageal cancer. Standard presurgical assessment with full medical history and physical examination, laboratory tests, cross-sectional imaging and cardiopulmonary assessment as determined by the operating surgeon or the Preoperative Anesthesia Clinic based upon RPCI established guidelines.

The following will be performed prior to the participant's scheduled minimally invasive esophagectomy and will be confirmed before surgery:

- Informed consent for study. Must be completed prior to receiving any study-related procedures.
- Medical history with preexisting conditions, including all neoadjuvant therapy related to esophageal carcinoma, smoking status and, diabetes.

- Physical examination, including vital signs (i.e., temperature, heart rate, respiratory rate, blood pressure), body weight and height; with emphasis on the neck, thoracic, and abdominal cavities.
- Multidisciplinary evaluation and neoadjuvant therapy if indicated for esophageal carcinoma. Multidisciplinary evaluation will be documented in the outpatient preoperative office visit note.
- Pregnancy test (urine) in females of childbearing potential. The standard operating procedure for all females of childbearing potential in the Ambulatory Surgical Center (ASC) pre-op holding area is to obtain a urine HCG. This study protocol does not deviate from the standard operating procedure of the ASC/pre-op holding area at RPCI. If the pregnancy test is positive, the patient is excluded from the study.
- Nutritional status assessment by a dietitian, as clinically indicated.

The following will be performed if indicated by the anesthesia pre-op assessment (standard operating procedure for the pre-op clinic at RPCI). These tests are not strictly required to support eligibility for this study, but if indicated and performed, may exclude the patient from receiving a general anesthetic and thereby excluding the patient from this study.

- Hematology: CBC with automated differentials (WBC, RBC, HGB, HCT, platelet, MCV, MCH, MCHC, % neutrophils, absolute neutrophils, % monocytes, absolute monocytes, % eosinophils, absolute eosinophils, % basophils, absolute basophils, % lymphocyte, absolute lymphocyte, platelet confirmation (as clinically indicated), and differential confirmation (as clinically indicated).

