6.5 Criteria for Retreatment

- Patients with “severe” delayed gastric emptying assessed radiographically or clinically at any time will be considered for endoscopic procedures for gastric outlet obstruction, including pyloric botulinum toxin injection or balloon dilation, or operative procedure. This is irrespective of whether a patient was initially treated with botulinum toxin at the minimally invasive esophagectomy; patients randomized to the botulinum toxin group may undergo additional botulinum toxin injection endoscopically. The maximum dose of botulinum toxin a patient may receive for this study in the three-month period is 300 units. Each of these procedures- when a patient undergoes a therapeutic endoscopic procedure or returns to the operating room- will be defined as a secondary procedure.
- Development of “severe” delayed gastric emptying as assessed by nuclear medicine study will be considered a failure of the experimental procedure and will be included in the primary analysis. Requirement for secondary procedure or development of “severe” delayed gastric emptying as assessed by parameters other than the nuclear medicine study will be included in the secondary analysis.
- Patients with “moderate” delayed gastric emptying assessed radiographically or clinically at any time will be considered for initiation of promotility agents. Development of “moderate” delayed gastric emptying will be included in the secondary analysis.

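### Section 7.1.2 says patients with underlying muscle weakness are excluded, but no exclusion criterion names it, so mainly stable primary muscle disease is left to the investigator's discretion

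*Combined protocol and SAP*

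**What the plan says.** Section 7.1.2 (Drug Information) describes swallowing and breathing difficulties after botulinum toxin as possibly life-threatening. It identifies a group at greater risk: "Patients with history of underlying conditions predisposing to muscle weakness have an increased risk of these side effects occurring". The next sentence says that "due to the nature of this study, patients with underlying muscle weakness are excluded from this study".

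Section 5.2 lists eight exclusions, and the Investigator Study Eligibility Verification Form repeats the same eight. The nearest to muscle weakness is Exclusion 1, which opens: "Patients who have a history of gastrointestinal dysmotility or functional gastroparesis, including diabetic gastroparesis, central and peripheral nervous system disorders". It goes on to renal failure and medication effects. Exclusion 8 is a general clause for any condition that in the investigator's "opinion deems the participant an unsuitable candidate for study participation".

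The baseline work-up in Section 6.2 includes "Medical history with preexisting conditions". On dose, Section 6.5 says: "The maximum dose of botulinum toxin a patient may receive for this study in the three-month period is 300 units". It allows repeat injection to be considered whatever the patient received at surgery. Section 7.1.2 gives the general ceiling: "The maximum recommended dose of OnabotulinumtoxinA, regardless of the indication, is 400 units over three months".

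**The concern.** Section 7.1.2 answers the extra risk in this group by stating, as a fact about eligibility, that the group is not in the trial. What decides enrollment is the form, where every exclusion must be answered no or not applicable. If the form never asks about muscle disease, staff can complete it correctly for a patient who has it, and the protection described in Section 7.1.2 does not operate as a rule.

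What is at stake is patient safety and the accuracy of the protocol put before the review board. Exposure is not confined to one arm, because a patient allocated to no injection may later be considered for endoscopic botulinum toxin. The effects of toxin spread that Section 7.1.2 lists, such as dysphagia and breathing difficulty, also resemble complications that the trial records after esophagectomy, such as aspiration and respiratory failure. A toxin effect in a susceptible patient could therefore be hard to recognize.

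**Working it through.** The plan gives no figure to reproduce. The check is a reading of every eligibility rule against the statement in Section 7.1.2.

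**Step 1. The eight exclusions (Section 5.2; identical on the form).**

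| No. | Subject | Names muscle weakness, myopathy or neuromuscular junction disease? | Cover it could give |
|---|---|---|---|
| 1 | Gut dysmotility or gastroparesis, with a list that includes nervous system disorders | No | Partial: neurogenic weakness, if the list item is read on its own |
| 2 | Earlier surgery on the stomach or duodenum | No | None |
| 3 | Duodenal ulcer or fibrosis | No | None |
| 4 | Uncontrolled illness (open-ended list) | No | Partial: muscle disease that is uncontrolled |
| 5 | Allergy to botulinum toxin or egg | No | None |
| 6 | Pregnancy or nursing | No | None |
| 7 | Unwilling or unable to follow the protocol | No | None |
| 8 | Investigator judges the patient unsuitable | No | Discretionary |

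The count is 0 of 8 naming the condition in Section 5.2, and 0 of 8 on the form.

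**Step 2. How far Exclusion 1 reaches.** The phrase "central and peripheral nervous system disorders" stands in a list introduced by the word including, after dysmotility and functional gastroparesis and beside renal failure and medication effects. By its grammar it names causes of dysmotility, so it excludes a patient only when dysmotility is present. Read as a separate item, it catches neurogenic weakness, including motor neuron disease. On either reading it does not cover primary muscle disease, and it does not clearly cover disorders of the neuromuscular junction.

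**Step 3. Other rules.**
- Inclusion criteria: the ECOG limit of 2 removes patients whose weakness is markedly disabling. Nothing else there bears on the point.
- Section 6.2: tests prompted by the anesthesia assessment may rule out a general anesthetic and so rule the patient out of the trial. This catches some severe disease.
- Appendix B: lists drugs only.
- Section 6.2, medical history: would probably reveal a known muscle disease, but no criterion makes that finding excluding.

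**Step 4. What remains.** Taking away what Exclusions 1 and 4, the ECOG limit and the anesthesia assessment can catch leaves a patient fit for esophagectomy with stable primary muscle disease, and possibly one with stable neuromuscular junction disease. For that patient the only applicable criterion is Exclusion 8.

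**Step 5. A comparison within the protocol.** Section 7.1.2 also names hypersensitivity as a contraindication, and Exclusion 5 carries that into the criteria. The muscle-weakness statement in the same section was not carried over.

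**Step 6. Scale of exposure.**
- Injected at surgery under 1:1 allocation: 50 / 2 = 25 patients, against all 50 under the center's standard operation (Section 4.1).
- Study dose cap against the stated general maximum: 300 / 400 = 75%.

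These figures describe exposure and do not measure the gap. The documents give neither the prevalence of muscle disease nor a rate of toxin spread, so no probability of enrollment or harm can be computed.

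**The case against.** The best defense is that the patient is already kept out in practice. Exclusion 1 may be the very exclusion that Section 7.1.2 has in mind, since a gastric-emptying trial would naturally exclude neurological causes of dysmotility. Exclusion 4, the ECOG limit and the anesthesia assessment remove further patients. An investigator who applies Exclusion 8 has the sentence in Section 7.1.2 as written direction. That section also offers other reassurance: at 100 units the toxin is not expected to reach the peripheral blood, spread is rare, and side effects depend on the injection site. It does not call muscle weakness an absolute contraindication.

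Most of this stands, and it narrows the point. A reader might infer that a patient with any muscle weakness is kept out only by Exclusion 8. The documents do not support that, because the other routes give partial cover. A reader might also infer that the trial creates a new hazard. At surgery it does not: injection is the center's standard, and allocation halves its use.

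The defense does not close the gap. None of the partial routes reaches stable primary muscle disease. A discretionary clause, even one read with Section 7.1.2, is weaker than the flat statement that these patients are excluded.

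**Conclusion.** The point holds in a limited form. Section 7.1.2 states a safety property that the eligibility criteria secure only in part. The uncovered group is mainly patients with stable primary muscle disease and possibly those with neuromuscular junction disease.

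Expected harm is small: spread is described as rare, the study cap is 75% of the stated maximum dose, and a routine history would probably bring out known disease. That last judgment is an assumption, as is the expectation that few such patients come to esophagectomy, because the documents give no rates. No statistical property of the trial is affected.

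It is tempting to conclude that Exclusion 1 should be rewritten so that every central or peripheral nervous system disorder excludes in its own right. Section 7.1.2 does not say that. Such a rule could remove, for example, patients with diabetic neuropathy, although diabetes is a stratification factor (Section 9.2). Accrual of 50 patients is already expected to take up to 6 years (Section 4.2), and the loss from so broad a rule has not been examined.

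**What to change.** Add one exclusion to Section 5.2 and the same line to the eligibility form, for example: *known myopathy, neuromuscular junction disorder or other underlying condition predisposing to muscle weakness*. The investigators should settle the final wording. Leave Exclusion 1 as it is.

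If the investigators do not intend this exclusion, correct the sentence in Section 7.1.2 instead. That is the weaker choice, because it withdraws a stated safeguard.

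The cost is a short amendment in two places. Loss of accrual should be negligible, since Section 7.1.2 already treats these patients as excluded.
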